Subgroup Analysis: The general approach to assessing the homogeneity of a treatment effect across subgroups will be to include an interaction term between the use of airway management strategy (standard versus initial SGA) and the characteristics defining the subgroup in the regression model. A statistically significant interaction term would indicate that the null hypothesis of a homogenous effect can be rejected, indicating a differential effect from airway management strategy across the subgroups. For example, when examining the homogeneity of the effect of airway management strategy on the primary outcome among those with and without a TBI, the logistic model will be modified to include a main effect for TBI and the two-

way interaction between airway management strategy and TBI.

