2.6.2 Sample Size Determination

This stepped wedge randomized control trial will use 24-hour mortality as its primary outcome to power the trial. This sample size was calculated using the formula presented by Hemming and Taljaard and takes into account the design feature that airway management strategy will be switched from standard care to initial SGA sequentially by 17 prehospital agencies over 7 time periods (6 steps).¹⁷ The intra-randomization unit correlation coefficient (ICC) for the primary outcome was assumed to be 0.025 based on preliminary data from Pittsburgh's prehospital agencies. To detect a decrease from 16.7% to 9.7% (a difference of 7%), with 80% power at 5% significance level, a sample size of 1,904 will be required. To account for 5% dropout, we will need to enroll 118 participants from each of the 17 prehospital agencies over the seven enrollment periods (17 participants per agency per period). Therefore, the total required sample size is 2,006, however, to enroll equal numbers of patients in each enrollment period, we will enroll 2,009 patients.

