2.6.3 Predefined Subgroups

Predefined subset analyses will be performed on: 1) participants with drug assisted advanced airway management, 2) participants treated by air medical services as compared to ground services, 3) services with video laryngoscopy, 4) participants with significant traumatic brain injury (Head Acute Injury Score (AIS) > 2) versus those without significant brain injury (Head AIS ≤ 2), 5) participants enrolled from the scene of injury versus those enrolled from a referral hospital, 6) participants who suffered blunt injury as compared to those who suffered penetrating injury, 7) participants with high versus low field to ED transport times (median split subgroups), 8) participants with BLS airway management prior to arrival the of the PACT participating agency, and 9) participants that were in arrest at the time of enrollment that achieved return of spontaneous circulation (ROSC).

We recognize that the trial is not appropriately powered for these subgroup comparisons; therefore, the results and conclusions formulated from these subgroup analyses will be considered exploratory in nature and will not be used as a basis for treatment recommendations.

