2.6.6 Interim Analyses

Prior to initiation, and in concert with the DSMB, the final monitoring plan will be developed to serve as a guide to the DSMB's decision-making process concerning early stopping of the trial. In making the decision to recommend termination of the trial, the DSMB will be guided by information on safety outcomes by treatment group.

Two interim safety analyses will be conducted, one at the completion of the second step (third period) and one at the completion of the fourth step (fifth period, out of seven periods). The frequency of the composite safety outcome (mortality, failure to place an advanced airway on first attempt, failure to

ventilate) in the two groups will be summarized. The null hypothesis that there is no difference in the proportion of the rate of the composite safety outcome between the two groups will be tested using a generalized linear mixed model. Group sequential methods, such as a Lan and Demets approach with an O'Brien and Fleming spending function will be used to ensure that the overall type I error rate of 0.05 is maintained across the three tests (two interim and one final), with the majority of the type I error reserved for the final test. Based on the expected recruitment of 287 participants per period (2,009/7 periods), we expect a sample size of 861 for the first interim analysis (information fraction of 43%) and 1,435 for the second interim analysis (information fraction of 71%). For the first interim analysis the upper/lower boundaries will be ± 3.22 with a nominal alpha level of 0.001. The second interim analysis will have upper/lower boundaries of ± 2.42 with a nominal alpha level of 0.015. The final analysis will have upper/lower boundaries of ± 2.00 with a nominal alpha level of 0.045.

Further—and in relation to the interim safety analyses—safety data by group will be provided periodically to the DSMB. Safety data serious adverse events include frequency, a description of each event, and the date of each event.

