2.6.9 Data Elements

Prehospital Elements: To include (but not be limited to) scene time, vital signs, times and description of prehospital interventions, procedure type(s), device type(s), airway adjuncts used, rapid sequence intubation, associated medications and dosages used, number of procedure attempts, reason for failed attempt(s), progression to surgical airway, time to successful airway management, time to advanced airway, procedure complications, time and dose of any medications administered (for induction, post intubation sedation, and resuscitation), transport time, vital signs during transport, times and description of interventions provided during transport, and mode(s) of transport (e.g. ground, air). Also includes provider level data—including level of training—and system level data, including staffing, service volume, frequency of airway management, and ambulance location (rural/urban).

In-Hospital Elements: To include (but not be limited to) relevant vital signs, relevant laboratory studies (including arterial blood gases), and interventions (especially time to extubation and/or reintubation as applicable). Ventilator associated pneumonia, post-traumatic acute respiratory distress syndrome (ARDS), and patient disposition will also be collected.

Outcome Elements: To include (but not be limited to) 24-hour survival, hospital length of stay, length of stay in ICU, ventilator days, and in-hospital survival through day 30.

Exploratory Analyses: To include (but not be limited to) associations that may represent the underlying mechanisms associated with airway management's effect on 24-hour survival. When the necessary data are available, we will examine time to definitive airway, exposure to hypoxia,

superoxia, hypotension, hypocarbia and hypercarbia. Exposure will be examined as a categorical value and as a continuous variable calculated as a function of depth (calculated from a given normal value) times duration. The value of this expression will be regressed to look for an association with mortality.

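### Transport time is cut at its sample median for a predefined interaction test. A continuous term would usually use the collected data better, by an amount that depends on inputs the plan does not state.

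*Combined protocol and SAP*

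**What the plan says.** Section 2.6.3 (Predefined Subgroups) lists nine subgroups. Item 7 is "participants with high versus low field to ED transport times (median split subgroups". The subgroup paragraph of section 2.6.1 gives one method for all of them: "include an interaction term between the use of airway management strategy (standard versus initial SGA) and the characteristics defining the subgroup in the regression model". Its worked example, for brain injury, adds a main effect and a two-way interaction to the logistic model for the primary outcome.

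The underlying measure is on file. The prehospital list in section 2.6.9 includes "transport time, vital signs during transport". The exploratory paragraph of the same section plans both a categorical and a continuous form for exposures such as hypoxia and hypotension. No continuous form is named for transport time.

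Section 2.6.3 then limits the claims: "We recognize that the trial is not appropriately powered for these subgroup comparisons", and the results "will be considered exploratory in nature and will not be used as a basis for treatment recommendations".

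**The concern.** Most of the other subgroups are naturally binary (air or ground, blunt or penetrating, scene or referral hospital), and head injury is divided at a stated AIS value. Transport time is the only one cut at a point set by the final sample. No value in minutes and no rationale is given. The median will depend on which agencies enrol and on their mix of air and ground transport, so it will not be known until enrolment ends.

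Patients just either side of the median are treated as opposites, while very short and moderate times are treated as the same. An interaction test that the plan already calls underpowered may lose more power, and the resulting high/low contrast is hard to carry over to an EMS system with different times. At stake is the usefulness of one exploratory analysis.

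**Working it through.** **1. The plan's own figure.** The design is first confirmed, because the simulation in step 4 uses it. Inputs from section 2.6.2: 16.7% versus 9.7%, 80% power, 5% significance, ICC 0.025, 17 agencies, 7 periods, 6 steps, 5% dropout. Two-sided testing is inferred from the symmetric boundaries in section 2.6.6 ("The final analysis will have upper/lower boundaries of ± 2.00 with a nominal alpha level of 0.045").

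- Individually randomised size per arm, with mean rate 0.132: [1.96 × √(2 × 0.132 × 0.868) + 0.8416 × √(0.167 × 0.833 + 0.097 × 0.903)]² / 0.07² = 365.9, so 366 per arm and 732 in total.
- Stepped-wedge factor with m = 16 per agency-period: [1 + 0.025 × (6 × 16 + 16 − 1)] / [1 + 0.025 × (3 × 16 + 16 − 1)] × 3 × 0.975 / [2 × (6 − 1/6)] = (3.775 / 2.575) × 0.2507 = 0.3676.
- 732 × 0.3676 × 7 periods ≈ 1,883. Divided by 7 × 16 = 112 per agency, this is 16.8 agencies, so 17 suffice. With m = 15 it would take 17.8.
- 17 × 7 × 16 = 1,904, as stated ("with 80% power at 5% significance level, a sample size of 1,904 will be required"). Dropout: 112 / 0.95 = 117.9, so 118 per agency, and 118 × 17 = 2,006, also as stated.

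The documents give no transport-time distribution, interaction size or interaction power. Steps 2 to 5 therefore rest on assumptions, shown as ranges.

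**2. Information retained.** For a linear interaction, the split retains a share r equal to the squared correlation between the measure and its median indicator.

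| Shape on the analysed scale | r | Loss |
|---|---|---|
| Uniform | 0.75 | 25% |
| Normal (e.g. log-time) | 2/π = 0.637 | 36% |
| Gamma, shape 4 | 0.594 | 41% |
| Exponential | 0.480 | 52% |

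A log-normal time whose effect is linear in minutes rather than log-minutes would lose more (48% at a log-SD of 0.5). Analysed and acting on the log scale, it is the normal case.

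**3. Power.** If the continuous test has power P, the split has Φ((1.96 + z_P) × √r − 1.96). For P = 80% and r = 0.637: (1.96 + 0.8416) × 0.798 − 1.96 = 0.275, which gives 61%.

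| Continuous | Median split | Points lost |
|---|---|---|
| 10% | 7.8% | 2 |
| 20% | 14.3% | 6 |
| 30% | 20.8% | 9 |
| 35% | 24.1% | 11 |
| 50% | 34.6% | 15 |
| 70% | 50.9% | 19 |
| 80% | 60.8% | 19 |
| 90% | 73.4% | 17 |
| 95% | 82.0% | 13 |

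At 80% continuous power, the loss is 12 points for a uniform measure and 31 for an exponential one.

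**4. Simulation of the design.** 17 agencies × 7 periods × 16 patients, 4,000 runs per setting. The agency effect has SD 0.5 on the logit scale (0.25 × 0.132 × 0.868 ≈ 0.029 as an ICC, close to 0.025). The modifier is normal with a linear effect. The logistic model has agency and period effects.

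| Log-odds gradient per SD | Continuous | Median split |
|---|---|---|
| 0.15 | 19% | 14% |
| 0.25 | 45% | 32% |
| 0.35 | 73% | 53% |
| 0.45 | 90% | 73% |

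With 40% of the time variance between agencies: 17% to 12%, 42% to 28%, 66% to 46%, 86% to 67%. The losses, 5 to 20 points, agree with step 3 within simulation error (at most 0.8 points per power estimate).

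For scale, the whole planned effect is ln(0.097/0.903) − ln(0.167/0.833) = −0.62. A gradient of 0.45 per SD would cancel it at 0.62 / 0.45 = 1.4 SD from the mean, while 0.15 would do so only at about 4 SD. The larger gradients are therefore large interactions.

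**5. The reverse case.** If the true modification is a step at the median, the same squared correlation works against the continuous term. In an 800-run simulation with a step of ±0.3 log-odds, the split had 56% power and the continuous term 38%. The formula agrees: (1.96 + 0.151) × 0.798 − 1.96 = −0.276, which gives 39%.

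**The case against.** The strongest reply is that nothing decisive depends on this. It is one of nine subgroups, all declared exploratory and underpowered. With small interactions both tests are weak, and changing the scale gains only a few points. A median rule fixed in advance is set without reference to outcomes, gives balanced groups and is easy to read. It is also the better test if the true effect is a threshold near the median, and the documents do not say which shape is expected. The simulation uses fixed agency effects and no baseline covariates, whereas section 2.6.1 specifies a random agency effect with covariates.

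Much of this stands. A reader might infer that the split always discards over a third of the information and always costs 10 to 20 points of power. The documents do not support that, because they give neither the distribution nor the interaction size, and the ordering can reverse. A reader might also infer that the trial could then say nothing about how the effect varies with transport time. That goes too far: the time is collected, and the exploratory list in section 2.6.9 is open-ended.

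The exploratory label calls for cautious interpretation. It gives no reason to coarsen a measure already in hand, and the plan offers none for expecting a step exactly at the sample median. The simulation's model choice applies equally to both forms of the modifier, and the closed-form result, which does not use that model, gives the same comparison.

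**Conclusion.** The point holds as a small improvement. For a modifier that is normal on the analysed scale with linear modification, the median split loses about 36% of the information and about 2 to 19 points of interaction power: 2 to 9 when the continuous test has 10% to 30% power, 11 to 19 when it has 35% to 95%. Since the plan concedes low subgroup power, the lower part of that range is at least as relevant as the upper. Across uniform to exponential shapes the information loss is 25% to 52%. The conclusion rests on effect modification being gradual rather than a step at the median.

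It would be wrong to read this as a threat to the trial's main result. The primary analysis, the 1,904 and 2,006 figures and the basis for treatment recommendations are unaffected.

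**What to change.** In section 2.6.3, item 7, define the interaction test as strategy by continuous transport time on the log scale, with its main effect, in the model already given in section 2.6.1. Add a restricted cubic spline to check linearity and detect threshold shapes. Report the estimated strategy effect, with confidence intervals, at times in minutes that the sponsor fixes in advance. Sample percentiles would depend on the enrolled agency mix just as the median does. Keep the median-split table as a description without a test.

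The cost is a few lines of SAP text, with no new data, patients or procedures. The downside is a linearity assumption, with some loss of power if the true modification is a threshold at the median.

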2.6.4 Enrollment of Ineligible Patients

It is anticipated that there will be a small proportion of patients who are deemed eligible by a participating EMS agency and treated with the intent to enroll but are later determined to have been ineligible. In this circumstance, an intent to treat principle will be followed, dictating that their data be analyzed according to the intended arm of treatment. Subgroup analyses based on eligibility criteria will be performed if the number of ineligible patients is large.

2.6.5 Non-Adherence

In some circumstances, subjects may receive standard care instead of an initial SGA when on the treatment arm. In keeping with the intention-to-treat analytic design, these participants will be analyzed according to the intended arm of treatment.

2.6.6 Interim Analyses

Prior to initiation, and in concert with the DSMB, the final monitoring plan will be developed to serve as a guide to the DSMB's decision-making process concerning early stopping of the trial. In making the decision to recommend termination of the trial, the DSMB will be guided by information on safety outcomes by treatment group.

Two interim safety analyses will be conducted, one at the completion of the second step (third period) and one at the completion of the fourth step (fifth period, out of seven periods). The frequency of the composite safety outcome (mortality, failure to place an advanced airway on first attempt, failure to

ventilate) in the two groups will be summarized. The null hypothesis that there is no difference in the proportion of the rate of the composite safety outcome between the two groups will be tested using a generalized linear mixed model. Group sequential methods, such as a Lan and Demets approach with an O'Brien and Fleming spending function will be used to ensure that the overall type I error rate of 0.05 is maintained across the three tests (two interim and one final), with the majority of the type I error reserved for the final test. Based on the expected recruitment of 287 participants per period (2,009/7 periods), we expect a sample size of 861 for the first interim analysis (information fraction of 43%) and 1,435 for the second interim analysis (information fraction of 71%). For the first interim analysis the upper/lower boundaries will be ± 3.22 with a nominal alpha level of 0.001. The second interim analysis will have upper/lower boundaries of ± 2.42 with a nominal alpha level of 0.015. The final analysis will have upper/lower boundaries of ± 2.00 with a nominal alpha level of 0.045.

Further—and in relation to the interim safety analyses—safety data by group will be provided periodically to the DSMB. Safety data serious adverse events include frequency, a description of each event, and the date of each event.

2.6.7 Handling Missing Data

The general strategy for missing data will concentrate on a tactical approach rather than only on an analytical one. The goal is to prevent missing data as much as possible because there is no analytical methodology that can recover the robustness and unbiased character of estimates derived from a complete case scenario. We expect very little missing data due to the nature of the trial design and related preparation and efforts to realize a well-conducted clinical trial. Because the intervention spans a short time and takes place mostly during the prehospital phase, we do not expect a considerable dropout during the treatment phase. Because we expect about 5% dropout, we have inflated the sample size by 5% to reduce the related effect on power adequacy.

For interim and final analyses, we will use multiple imputation for the final value for participants whose 24-hour mortality cannot be determined. For sensitivity analyses, we will report the data with and without multiple imputation. We will also report an analysis consistent with that used in other trauma studies, which count those with missing data as 'alive' and 'dead' using the overall mortality rate for the trial at 24 hours. Missing data will be documented along with the related causes, continuously monitored, and mitigated accordingly. The electronic data management system prevents study personnel from skipping questions and requires an appropriate missing data code. We will assume that data are not missing at random. A likelihood-based analysis, including regression, multiple imputations, and random-effects regression models could be implemented in this regard. Missing outcomes can be predicted from individuals' observed data using models based on observed individuals. The final analyses will explicitly state the assumptions underlying the treatment of missing outcomes and explain the use of compressive data descriptions and sensitivity analysis. Sensitivity analysis will allow us to explore the robustness of conclusions compared to alternative plausible assumptions. We will follow the CONSORT statement in reporting the number of randomization units with missing outcome data by treatment arm.¹⁸ All methods used in treating missing data will be adequately reported.²²

2.6.8 Data Management

Data Sources: Data will be collected prospectively while care progresses and abstracted later from patient records. Abstraction will include a review of the ground and air medical patient care report(s), emergency department records, and hospital records, both electronic and on paper.

Data Entry: The DCC will create an electronic data management system that will include a password protected SSL website for data entry by participating sites with built in dynamic features such as data encryption, user authentication, range and data type checks, real time reports, data corrections tracking, and the capability to save and reload incomplete forms. The DCC will also draft a comprehensive data management manual that includes detailed instructions and provide training and technical assistance. Subjects will be identified by a study ID only. Sites will be required to store hard copy source documentation separately in a secured, locked cabinet.

Database Management: A two-tiered database structure will be created. A front-end database will serve the needs of web entry at the sites, using a database management system well suited to handling updates from multiple interactive users. The data from this database will be transferred on a regular schedule to a data repository that can be used by statistical software packages. These data sets will be the basis of data queries and monitoring reports. Various versions of this database will be kept as needed, such as for quarterly performance reports. Access to data will be limited to those who need access to perform their tasks. The database management system can manage large quantities of data, merge data from multiple databases as required, handle complex and possibly changing relationships, and produce analysis datasets that can be imported into a variety of statistical analysis packages. Data will be backed up at regular intervals, with full transaction log files in use, and copies of the data will be stored offsite with a secure service. Servers will be migrated to a new host in the event of a hardware failure. All servers are behind an enterprise firewall and access must be granted through the firewall even within the University network.

2.6.9 Data Elements

Prehospital Elements: To include (but not be limited to) scene time, vital signs, times and description of prehospital interventions, procedure type(s), device type(s), airway adjuncts used, rapid sequence intubation, associated medications and dosages used, number of procedure attempts, reason for failed attempt(s), progression to surgical airway, time to successful airway management, time to advanced airway, procedure complications, time and dose of any medications administered (for induction, post intubation sedation, and resuscitation), transport time, vital signs during transport, times and description of interventions provided during transport, and mode(s) of transport (e.g. ground, air). Also includes provider level data—including level of training—and system level data, including staffing, service volume, frequency of airway management, and ambulance location (rural/urban).

In-Hospital Elements: To include (but not be limited to) relevant vital signs, relevant laboratory studies (including arterial blood gases), and interventions (especially time to extubation and/or reintubation as applicable). Ventilator associated pneumonia, post-traumatic acute respiratory distress syndrome (ARDS), and patient disposition will also be collected.

Outcome Elements: To include (but not be limited to) 24-hour survival, hospital length of stay, length of stay in ICU, ventilator days, and in-hospital survival through day 30.

Exploratory Analyses: To include (but not be limited to) associations that may represent the underlying mechanisms associated with airway management's effect on 24-hour survival. When the necessary data are available, we will examine time to definitive airway, exposure to hypoxia,

superoxia, hypotension, hypocarbia and hypercarbia. Exposure will be examined as a categorical value and as a continuous variable calculated as a function of depth (calculated from a given normal value) times duration. The value of this expression will be regressed to look for an association with mortality.

